### **3.2 Primary Study Endpoints**

The primary endpoints to be measured include:

- Self-report ratings of cues, subjective ratings of craving during/following cue exposure, and neuroimaging data on cerebral blood flow when the brain is at rest and when exposed to alcohol cues.

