### **6.3 Laboratory/MRI Session 1 Visit (approximately 3.5 hours)**

Interested, eligible, consented subjects will attend the first of two laboratory/MRI session visits. Prior to each scan visit, subjects will be instructed not to drink alcohol for 24 hours before the scheduled scan session. Upon arrival, subjects will be breathalyzed to ensure that they have not recently consumed alcohol (BrAC = 0.00 g%). During this visit, subjects will complete: 1) brief questionnaires (see Table of Assessments), 2) CogState and CogBias computerized tasks (described below), 3) females will take a urine pregnancy test and provide a blood sample (approximately 2 tablespoons) for biochemical verification of menstrual cycle phase, 4) an MRI scan, and 5) following the scan, a brief medical management session with a nurse to receive medication.

Prior to MRI scanning, subjects will meet with study staff who will conduct the CIWA-Ar and prepare the subject for the MRI session. Subjects will also be asked to drink to satiety prior to starting the scan session to avoid potential confounding effects of thirst on neural responses to cues. During the scanning session, subjects will be asked to lie still with their eyes open for a 5 minute resting baseline scan, followed by two 10-minute audio-visual clips consisting of either alcohol-related cues: individuals differing in race, age and sex who are drinking alcohol and using explicit language designed to induce appetitive desire for alcohol; or non-alcohol-related cues that are similar in content, but individuals relate interesting short stories that do not portray alcohol consumption or alcohol reminders. Subjects will also be asked their level of alcohol craving (on a scale from 0-10) before and after each audio-video clip. Following the scan session, subjects will meet with a nurse to receive their first week of medication and the initial medical management session (see below).

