#### 7.2.2 Imaging Data Analyses

Global CBF time course will be included in the model as a covariate to examine the effects of topiramate on regional CBF. No temporal smoothing will be applied. Contrasts between conditions (alcohol cue vs non-alcohol cue; scan 1 vs scan 2) will be defined in the general linear model to assess the voxel by voxel CBF difference. Using the corresponding parametric maps of this contrast ( $\beta$  maps), random effects analysis will be employed to test for a significant main effect of condition with a statistical parametric map of the T statistic at each voxel for population inference for each session for the placebo and topiramate groups (second-level analysis). A 2x2 factorial design matrix will be used to assess the effects of the pharmacological manipulation by including the group (topiramate vs placebo) and condition (scan 1 vs scan 2) as the two factors. An associated contrast will be defined in this model to examine administration effects. This two-stage analysis is theoretically equivalent to a 2-way analysis of variance (ANOVA). Simple regression analyses will be conducted on CBF with the change in craving scores [post-alcohol cue minus pre-alcohol cue craving scores, number of heavy drinking days during the past 30 days, and age] as covariates of interest to test for prognostic brain/behavioral correlations. For the exploratory aim, subjects will be grouped by genotype (CC vs A-allele carrier) to examine the moderating effects of rs2832407 in

CONFIDENTIAL

This material is the property of the University of Pennsylvania. Do not disclose or use except as authorized in writing by the study sponsor

*GRK1* on topiramate effects using the same simple regression analyses described above. We will limit this analysis to European Americans, as that is the population in which the preliminary findings were obtained and allele frequencies differ significantly by population.

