### **7.2.3 Behavioral Analyses**

Statistical significance tests use an alpha of .05 unless otherwise noted. Continuous demographic variables (e.g., age, education, quantity/frequency of alcohol use) are checked for normality, transformed if necessary, and summarized by calculating means, standard deviations and ranges. Scores on each factor will be included as covariates of interest with respect to perfusion fMRI data and genetic variance. Analysis of variance will be used to assess demographic differences across groups. Nominal demographic variables (e.g., race, sex, genotype) are summarized by calculating proportions and compared across groups using chi square analyses. Demographic (age, years education, monthly income) and clinical (depression, anxiety) will also be summarized.

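### Cue-induced craving is a listed primary endpoint, but the plan specifies no topiramate-versus-placebo analysis of it and leaves the non-alcohol-clip craving ratings unused

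*Combined protocol and SAP*

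**What the plan says.** Section 3.2 includes "subjective ratings of craving during/following cue exposure" among the primary endpoints, beside ratings of the cues and CBF at rest and under cues. Section 6.3 sets out the collection: "Subjects will also be asked their level of alcohol craving (on a scale from 0-10) before and after each audio-video clip". With one alcohol and one non-alcohol clip that is four ratings per scan, and section 6.5 repeats the procedure at Scan 2.

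The analysis text uses part of this. In section 7.2.2 the craving variable is the "change in craving scores [post-alcohol cue minus pre-alcohol cue craving scores", entered with heavy drinking days and age "as covariates of interest to test for prognostic brain/behavioral correlations". The pilot analysis in Appendix 14.9.2 defines craving change the same way. For CBF, section 7.2.2 says "Contrasts between conditions (alcohol cue vs non-alcohol cue; scan 1 vs scan 2) will be defined in the general linear model", and its group-by-scan model, "including the group (topiramate vs placebo) and condition (scan 1 vs scan 2) as the two factors", belongs to that voxel-wise analysis. In section 7.2.3 the between-group statement for continuous variables is "Analysis of variance will be used to assess demographic differences across groups", with chi-square tests for nominal demographics. Behavioural scores otherwise appear there only as covariates for the imaging and genetic data.

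**The concern.** Two gaps follow. First, a primary endpoint in a randomised, placebo-controlled comparison has no planned comparison between the arms. Any later test of topiramate on craving would be post hoc, although section 1.1 promises behavioural as well as brain mechanisms and cites reduced craving in its rationale.

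Second, the study collects a within-session control for craving and does not use it. Ten minutes in a scanner can move a craving rating through time, discomfort or repeated asking. The alcohol-clip change contains that movement as well as any response to the cue. This matters in three places: confirming a behavioural cue response (Objective 1); the craving/CBF correlations, if the movement differs between subjects; and any arm comparison on the alcohol-only score, if topiramate alters general state. Section 1.4 lists fatigue, sleepiness and nervousness among its side effects.

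**Working it through.** **What the plan assigns to craving.** The plan has four places where an arm comparison of craving could sit. The 2x2 group-by-scan model is stated for CBF. The simple regressions have CBF as outcome and craving as predictor. Section 7.2.3 tests demographics. The Study Summary names frequencies, descriptives and voxel-wise CBF analyses. None has craving as an outcome, and none uses the non-alcohol-clip ratings. Sections 7.1 and 14.8.1 base sample size on piloting the videos, so there is no planned figure to reproduce.

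Every variance and drift below is an assumption on the 0-10 scale; the documents give none.

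**1. Objective 1: is there a cue response?** Suppose the true cue effect is zero, mean drift is m, drift SD is 1 between subjects and rating noise SD is 1 per change score. The alcohol-only change then has SD √(1+1) = 1.414, and a one-sample t test has noncentrality m√n/1.414.

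- m = 0.5: noncentrality 1.58 at n = 20 and 2.24 at n = 40; rejection about 32% and 59%.
- m = 1.0: noncentrality 3.16 and 4.47; rejection about 85% and 99%.

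If drift is the same in both clips, subtracting the non-alcohol change removes it and rejection stays near 5%.

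**2. Craving/CBF correlation.** Assume cue-specific craving SD 2 (variance 4), rating-error variance 1 per change score, drift variance v, and a true correlation with CBF of 0.50. Then r = 0.5·√(4/(4+V)), where ρ is the correlation of drift between clips and

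- alcohol-only: V = v + 1
- non-alcohol change as added covariate: V = (v+1) − (ρv)²/(v+1)
- net score by subtraction: V = 2v(1−ρ) + 2

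| v | Alcohol-only | Covariate, ρ=1 | Net, ρ=1 | Covariate, ρ=0.5 | Net, ρ=0.5 |
|---|---|---|---|---|---|
| 0 | 0.447 | 0.447 | 0.408 | 0.447 | 0.408 |
| 1 | 0.408 | 0.426 | 0.408 | 0.413 | 0.378 |
| 2 | 0.378 | 0.420 | 0.408 | 0.387 | 0.354 |
| 4 | 0.333 | 0.415 | 0.408 | 0.349 | 0.316 |

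With ρ = 1 and v of 1 to 4, the covariate version gains 0.02 to 0.08. With ρ = 0.5 it gains 0.005 to 0.016. The sampling error of a correlation near 0.38 at n = 40 is about (1−0.378²)/√39 = 0.14. Subtraction helps only when v(2ρ−1) exceeds 1, the assumed error variance; otherwise it loses precision.

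**3. Which arm model?** Let topiramate shift both Scan 2 changes by −1 point with no effect on the cue response.

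- Adjusting the alcohol change for the Scan 2 non-alcohol change uses the slope v/(v+1) (ρ = 1), so −1 × [1 − v/(v+1)] = −1/(v+1) remains: −0.50, −0.33 and −0.20 for v = 1, 2 and 4.
- The net score gives −1 − (−1) = 0.

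**4. What 20 per arm can show.** Two-sided alpha 0.05 is assumed, since sidedness is not stated. The difference detectable with 80% power is (1.96 + 0.84)·√(2/20) = 0.89 SD, or 0.91 SD by the t distribution. By the t distribution, power is 34% at 0.5 SD and 69% at 0.8 SD. An unadjusted 95% interval extends 2.024·√(2/20) = 0.64 SD either side of the estimate. Scan 1 adjustment narrows it to the extent that the two scans correlate.

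**The case against.** The best defence is context. The Study Summary calls this pilot and basic research, section 1.1 says it is not a treatment trial, and Hypotheses 2a and 2b concern neural activity, cue reactivity and heavy drinking without naming craving as a tested outcome. That lowers the stakes but does not remove the gap, because section 3.2 still lists craving as primary. The ratings are collected, so what is missing is a specified analysis, not the data.

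The alcohol-only score is also a defensible scoring choice in part. The pre-clip rating already removes each subject's starting level, including any effect of the 24-hour no-drinking instruction.

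Two stronger readings are tempting. A reader might infer that drift biases the planned regressions or would bias an arm contrast. A shift common to all subjects does neither: it moves the intercept, not the slope, and it cancels between randomised arms. Only drift that varies between subjects, or a drug effect on general state, does harm, and the documents quantify neither. A reader might also infer that the regressions pair a control-corrected brain signal with an uncorrected craving score. Section 7.2.2 says only that they are run on CBF. It does not say whether the outcome is the alcohol-versus-non-alcohol map, resting CBF or a scan difference, so that mismatch is plausible but not stated.

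Finally, section 6.3 gives neither clip order nor counterbalancing. If the alcohol clip came first, lingering craving could enter the non-alcohol change, and correcting for it could remove true signal. That caution stands.

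**Conclusion.** The concern holds in two parts. The firm part needs no assumption: a listed primary endpoint has no topiramate-versus-placebo analysis, and the control-clip ratings are not used anywhere in the plan. The second part, that the alcohol-only score is not cue-specific, is true by construction, but its consequences depend on unknown variances. They could be large for confirming a behavioural cue response. For the brain/behaviour correlations they are modest, and on the assumptions above smaller than the sampling error. For an arm comparison they arise only if topiramate changes general state. The documents do not support the claim that drift invalidates the planned regressions. The craving comparison should be added for estimation: with 20 per arm, only differences near 0.9 SD would be detected with 80% power.

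**What to change.** In section 7.2.3, define net cue-induced craving as the alcohol-clip change (post minus pre) minus the non-alcohol-clip change. Compare Scan 2 net craving between arms by ANCOVA adjusted for Scan 1 net craving, and report the difference with a 95% confidence interval. Do not adjust for the Scan 2 non-alcohol change: it is measured after randomisation and topiramate may alter it.

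In section 7.2.2, also run the craving/CBF regressions with control correction, keeping the alcohol-only score as a sensitivity analysis. Entering the non-alcohol change as an added covariate is safer here than subtraction on the figures above. State which CBF map is the outcome, and state the clip order in section 6.3.

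The cost is wording: no new data, visits or procedures. The covariate uses one degree of freedom. The net score loses some precision if between-subject drift is small or poorly correlated between the clips. Possible carry-over between clips remains a limitation to report.

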### **7.2.3 Behavioral Analyses**

Statistical significance tests use an alpha of .05 unless otherwise noted. Continuous demographic variables (e.g., age, education, quantity/frequency of alcohol use) are checked for normality, transformed if necessary, and summarized by calculating means, standard deviations and ranges. Scores on each factor will be included as covariates of interest with respect to perfusion fMRI data and genetic variance. Analysis of variance will be used to assess demographic differences across groups. Nominal demographic variables (e.g., race, sex, genotype) are summarized by calculating proportions and compared across groups using chi square analyses. Demographic (age, years education, monthly income) and clinical (depression, anxiety) will also be summarized.

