#### **1.4 Clinical Data to Date**

Topiramate has been evaluated for safety in over 3000 adults, and there are few serious adverse effects associated with topiramate. The most common adverse effect of topiramate compared to placebo is numbness and tingling (49% vs. 6%). The other most common side effects (experienced by 10-31% of patients) in clinical trials include: change in sense of taste, tiredness/sleepiness, fatigue, dizziness, loss of appetite, nausea, diarrhea, weight decrease, difficulty concentrating and difficulty with memory. Cognitive dysfunction adverse effects (e.g., confusion, psychomotor slowing, difficulty with concentration/attention, difficulty with memory, speech or language problems, particularly word-finding difficulties) that were reported during 6-month migraine prophylaxis studies (28% vs. 10% for placebo) were of mild-to-moderate severity. Other adverse effects (experienced by 5-9% of patients) in some clinical trials include: nervousness, slow thinking, abnormal vision, confusion, decreased sensitivity (hypesthesia), anxiety, abdominal pain, dry mouth, involuntary muscle contractions, and language problems. Depression and mood problems have also been reported (experienced by 5-9% of patients). Severe metabolic acidosis (decreased bicarbonate levels) is associated with topiramate treatment in 3-7% of individuals taking the medication.

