### **4.4 Early Withdrawal of Subjects**

#### **4.4.1 When and How to Withdraw Subjects**

Subjects with severe psychological symptoms (e.g., suicidal thoughts), those who fail to adhere to protocol requirements, and those withdraw consent will be withdrawn from the study and if applicable, referred for appropriate clinical care. If a subject is found to be pregnant during screening or during study, she will immediately be withdrawn from the study, referred for obstetric evaluation, and advised to discontinue all drinking.

Any subject experiencing a serious adverse event felt to be related to study drug should be withdrawn from the study.

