This material is the property of the University of Pennsylvania. Do not disclose or use except as authorized in writing by the study sponsor

(vocabulary and matrix reasoning) that offers an estimate of an individual's cognitive functioning. Individuals with an intelligence quotient of  $\leq 80$  are excluded because they do not have the cognitive skills necessary to participate in several of the study components.

j. **Beck Depression Inventory (BDI)**, a 21-item self-report measure of depressive symptoms, yields a total score that ranges from 0 to 63 (Beck et al. 1961). The BDI is generally regarded as a sensitive self-report measure of depressive symptoms and suicidal ideation.

k. **Menstrual Cycle Questionnaire (MCQ)** is a questionnaire administered by the Nursing Staff to all prospective female subjects that elicits information on menses status, menstrual cycle length, and premenstrual symptoms (PMS). This measure is acquired because hormone levels vary and cortical GABA levels decline from follicular to luteal phase of the menstrual cycle [43], and these changes influence CBF [44] and behavior [45]. Thus, this questionnaire (and progesterone/estrogen levels) will help us determine if females are pre-, peri- or post-menopausal.

ALL screening assessments will be performed to determine subject eligibility criteria, which will be documented. All subjects will also complete a practice round of cognitive testing with the CogState battery (described in detail below). The PI will confirm and sign off on the inclusion and exclusion criteria on a case report form (CRF) prior to the subject formally included in the study. Prospective subjects will be notified of their eligibility by telephone within 5 business days. This waiting period is necessary to examine results from the screening visit to determine whether the subject meets eligibility requirements.

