#### **6.4 Weekly Visits (approximately 50 minutes)**

At each weekly visit, subjects in both medication groups will receive medical management (MM) [33]. This provides a basic clinical intervention that was designed to be used in conjunction with prescribed medication, and to be easily implemented by medically trained practitioners in non-specialty settings. The treatment will support subjects' efforts to reduce their drinking.

The first session (conducted right after the first MRI scan) will consist of a review of the results of the initial evaluation, identifying any medical concerns. This session will also use the brochure *A Guide to Sensible Drinking*, developed for use in the World Health Organization Brief Intervention Study project. The subject is then provided with a rationale and information about pharmacotherapy and the importance of adherence. At each visit, assessment and counseling (lasting approximately 15 minutes) are conducted. During these sessions, the nurse will perform a medical check on the subject's general functioning, obtain vital signs and weight, ask about medication side effects and concurrent medications, monitor the subject's medication adherence, and as appropriate, make recommendations on strategies for medication adherence for the subject to follow until the next visit. Men will be advised to consume no more than 4 standard drinks per day and 12 standard drinks per week and women will be advised to consume no more than 3 drinks per day and 8 drinks per week. Because subjects will not be physically dependent on alcohol, reduction of heavy drinking is a safe and ethical goal. The research technician or coordinator will measure the subject's breath alcohol concentration, perform a brief assessment of the subject's drinking, review the self-administered BDI to assess suicidal thoughts/ideation (and discuss with the nurse and/or physician, if there is endorsement of suicidal thoughts). For patient safety during travel, subjects will be instructed not to drink prior to study visits. At each visit, the subject's BrAC, weight, and vital signs will be measured. Subjects must have a breath alcohol level of 0.00 g% to complete the screening visit, 2 lab MRI scan visits, and endpoint visit, and below 0.05 g% to complete the weekly study visits. Study staff will follow TRC standard operating procedures for all subjects that present with a breath alcohol level above 0.00 g% at study visits.

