### **Schedule of Assessments**

Instrument	Visit 0 Screening	Visit 1 MRI	Visits 2-6	Visit 7 MRI	Visit 8	Visit 9 Endpoint
Breath Alcohol Concentration & Vital signs	X	X	X	X	X	X
Study Overview & Informed Consent	X					
Medical History & Physical Exam	X					
Laboratory tests (Blood for CBC, GGTP, HIV and DNA)						X (GGTP only)
MRI video	X					
MRI safety sheet (metal)	X	X		X		
Urine pregnancy test	Females	Females		Females		
Urine drug toxic screen	X	X		X		
Blood sample (2 Tbsp)	Females	Females		Females		
Demographic interview	X					
Structured Clinical Interview for DSM	X					Alcohol Module Only
Wechsler Abbreviated Scale of Intelligence	X					
Timeline Follow-Back Interview	X	X(brief)	X(brief)	X(brief)	X(brief)	X(brief)
Beck Depression Inventory	X	X	X	X	X	X
Short Index of Problems	X			X		X

CONFIDENTIAL

This material is the property of the University of Pennsylvania. Do not disclose or use except as authorized in writing by the study sponsor

Fagerstrom Test of Nicotine Dependence	X					X
Obsessive Compulsive Drinking Scale	X	X		X		X
Alcohol Urge Questionnaire	X	X		X		X
Within Session Rating Scale		X		X		
Clinical Institute Withdrawal Assessment for Alcohol Scale	X	X		X		
CogBias Tasks		X		X		
Cogstate Battery		X		X		X
Controlled Oral Word Association test		X		X		
Digit Span		X		X		
Medical Management		X	X	X	X	X
Endpoint/Termination Form						X
Medication Questionnaire						X
Measures of Treatment		X	X	X	X	X

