## **8.2 Recording of Adverse Events**

At each contact with the subject, an investigator or staff member must seek information on adverse events by specific questioning and, as appropriate, by examination. Information on all adverse events should be recorded immediately in the source document, and also in the appropriate adverse event module of the case report form (CRF). All clearly related signs, symptoms, and abnormal diagnostic procedures results should be recorded in the source document, though should be grouped under one diagnosis.

CONFIDENTIAL

This material is the property of the University of Pennsylvania. Do not disclose or use except as authorized in writing by the study sponsor

All adverse events occurring during the study period must be recorded. The clinical course of each event should be followed until resolution, stabilization, or until it has been determined that the study treatment or participation is not the cause. Serious adverse events that are still ongoing at the end of the study period must be followed up to determine the final outcome. Any serious adverse event that occurs after the study period and is considered to be possibly related to the study treatment or study participation should be recorded and reported immediately.

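### The BDI is collected at every visit and mood problems are a stated topiramate risk, but Section 7 prespecifies no by-arm, over-time analysis of it, and the withdrawal and population rules would leave out those who worsen

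*Combined protocol and SAP*

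**What the plan says.** **The risk.** Section 1.4 states: "Depression and mood problems have also been reported (experienced by 5-9% of patients". No placebo rate is given for this item.

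**The data.** The Schedule of Assessments marks the "Beck Depression Inventory" in every column, Visits 0 to 9. Section 6.2, under the measures obtained, says: "The BDI is generally regarded as a sensitive self-report measure of depressive symptoms and suicidal ideation".

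**The analysis.** Section 7.2.3 says: "Demographic (age, years education, monthly income) and clinical (depression, anxiety) will also be summarized". The ANOVA and chi-square comparisons in the same paragraph are for demographic variables. Section 7 has no BDI-by-visit-by-arm analysis and no by-arm adverse event table.

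**Individual safety handling.** At weekly visits (6.4) staff "review the self-administered BDI to assess suicidal thoughts/ideation (and discuss with the nurse and/or physician, if there is endorsement of suicidal thoughts". Section 8.2 adds: "At each contact with the subject, an investigator or staff member must seek information on adverse events by specific questioning". Section 8.6 has adverse events monitored weekly.

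**Who leaves and who is analysed.** Those to be withdrawn under 4.4.1 include "Subjects with severe psychological symptoms (e.g., suicidal thoughts), those who fail to adhere to protocol requirements". Section 7.3 restricts analysis to protocol-compliant subjects and does not define the term. Section 6.5 asks those who stop early to complete the scheduled assessments so that intention-to-treat analyses are possible.

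**The concern.** The trial names a psychiatric risk of its own study drug and measures mood repeatedly with a suitable scale in a randomised, blinded design. Yet nothing in the plan requires those scores to be set side by side by arm over time. A summary of depression next to age, education and income could be met by one pooled baseline row.

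The second problem is selection. Withdrawal for severe psychological symptoms ends a subject's on-treatment scores because of the outcome being measured. A protocol-compliant set may then remove that subject altogether. If topiramate worsens mood, the loss falls more heavily on the topiramate arm, and the scores that remain make that arm look better than it was.

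A smaller point is that the sentence promises a summary of anxiety, for which no instrument appears in the measures or the schedule.

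**Working it through.** The plan gives no power, SD or effect size for the BDI, so there is no figure of its own to reproduce. The steps below size the issue.

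**Inputs from the documents.** 20 subjects per arm (5.3); mood problems in 5-9% (1.4); alpha 0.05 (7.2.3), taken as two-sided because sidedness is not stated; BDI at seven visits falling in the dosing period (Visits 2-8) and one after taper (Visit 9), from the Schedule and Table 1.

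**Assumptions.** Correlation between BDI scores of 0.3-0.7; a placebo mood-event rate of 3%, with 0% as the extreme.

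**1. Can event counts show a signal?**
- Expected events on topiramate: 20 × 0.05 = 1.0 and 20 × 0.09 = 1.8.
- Chance of none: 0.95^20 = 0.358 and 0.91^20 = 0.152.
- Fisher's exact test, 9% against 3%, 20 per arm: power 0.016. Against 0%: power 0.03.

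Counts alone are close to uninformative. With no placebo rate in 1.4, these are expected events on drug, not events caused by drug.

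**2. How much do the BDI scores add?** For a baseline-adjusted arm difference at one visit, in SD units, with r the correlation:

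half-width = t(0.975, 37) × √[(2/20)(1 − r²)], with t = 2.026.

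| r | 20 per arm |
|---|---|
| 0.7 | 2.026 × √0.051 = 0.46 |
| 0.5 | 2.026 × √0.075 = 0.55 |
| 0.3 | 2.026 × √0.091 = 0.61 |

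Dropout widens this. At 15 per arm and r = 0.7, it is 2.052 × √[(2/15)(0.51)] = 0.54 SD.

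For the mean of m = 7 dosing-period scores, (1 − r²) is replaced by (1 + 6r)/7 − r². At r = 0.5 this is 0.321, giving 2.026 × √0.0321 = 0.36 SD. At r = 0.7 it is 0.253, giving 0.32 SD. These assume 20 complete subjects per arm.

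**3. What does the selection remove?** Let a fraction p of the topiramate arm worsen and be left out, with mean BDI higher by D than the rest. The full-arm mean is then the retained mean plus pD. If every event at the 5-9% rate led to withdrawal and exclusion (an upper bound), the arm mean would be understated by 0.05D to 0.09D. The retained set would show no such events, where 1.0-1.8 were expected.

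**4. Does adverse event capture fill the gap?** Section 8.1 normally ends the reporting period about 2 weeks after consent. Section 3.1 gives 8 weeks of medication. Section 8.2 requires every event in the study period to be recorded. These three do not agree, so the completeness of mood events late in dosing is unclear.

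**The case against.** A reader might infer that a drug-related mood problem would go unreported, or that the 7.2.3 sentence is the only use made of the BDI. The documents support neither. Adverse events are sought by direct questioning at each contact and recorded (8.2), monitored weekly (8.6) and reviewed by the principal investigator at least weekly (10.1). Serious events go to the IRB within 72 hours (8.3.1). The weekly visit has staff "review the self-administered BDI to assess suicidal thoughts/ideation", and the Endpoint Visit (6.6) includes the BDI for the same purpose. The 7.2.3 sentence does not limit itself to baseline and does not forbid a summary by arm.

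Nor does the plan stop collecting data at withdrawal. Section 6.5 asks early terminators for an end-of-treatment evaluation and all scheduled assessments, and 4.4.2 adds follow-up effort. The route to exclusion is therefore the analysis set in 7.3, and the bias arises only if an on-treatment or protocol-compliant BDI table is produced.

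Proportion matters too. The protocol describes a pilot, mechanistic study and says it is not a treatment trial. Its primary endpoints are cue ratings, craving and cerebral blood flow.

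All of this stands, and it narrows the point. It does not remove it: the safety provisions deal with individual cases, and none prescribes a comparison between arms. The intention-to-treat data that 6.5 sets out to collect have no analysis in Section 7.

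**Conclusion.** The point holds in this form: no by-arm, over-time analysis of the BDI, and no by-arm table of mood adverse events, is prespecified. The withdrawal rule and the protocol-compliant set together would leave out subjects who worsened to the point of withdrawal, so a group-level mood effect could be missed or understated. That last step assumes that 7.3 is read to exclude withdrawn subjects, which its wording permits but does not define.

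The change should be made, but it does not threaten the primary objectives. Even when done well, the analysis yields an imprecise estimate: a half-width of about 0.46-0.61 SD at one visit with 20 per arm for assumed correlations of 0.7-0.3, and wider with dropout. An interval that includes zero would not be evidence of safety.

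**What to change.** In 7.2.3, keep the demographic summary, delete anxiety, and add:

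> BDI will be summarised by arm and visit and compared between arms in all randomised subjects who took study drug, as an exception to 7.3, using a repeated-measures model with arm, visit, arm-by-visit, the Visit 1 pre-drug BDI and the two randomisation factors (sex; number of heavy drinking days in the past month, above 12 or not). All available scores will be used, including those obtained after stopping drug under 6.5. Visits 2-8 (dosing period) will be reported separately from Visit 9 (after taper), as an estimate with 95% CI. The numbers newly endorsing the BDI suicidal-thoughts item, withdrawn for psychological symptoms, and with mood adverse events will be tabulated by arm.

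Naming Visit 1 as baseline settles which of the two pre-drug scores is used. Stating the exception to 7.3 avoids a new contradiction about the analysis population.

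Separately, the roughly 2-week adverse event reporting period in 8.1 must be reconciled with the 8 weeks of medication in 3.1 and with 8.2. Which period should apply is for the sponsor and the investigator to settle.

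The cost is plan wording, one model and one table from data already scheduled. No dose, visit, withdrawal or safety rule changes. The drawback is a wide interval, which should be presented as an estimate only.
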